#### **Intervention Modifications:**

We do not expect any safety-related issues that would necessitate removing a participant from either the PT-led or usual physician-led primary care pathway. In line with routine care practices for hip or knee pain, the primary care team will adjust the intervention as needed to prioritize participant well-being. Adjustments may be made in response to factors such as increased pain, limited mobility, poor tolerance to treatment, changes in clinical status, or adverse reactions to medications or exercises. As the risks are minimal and did not compromise participants' well-being, a data monitoring committee was not established.

#### **Data Collection and Management:**

All baseline measures have been collected from participants and follow-up data collection is ongoing. We used several approaches to support participant retention at all time points. Research assistants maintained regular contact, sending reminders every two to three days via personalized emails, phone calls, and text messages to encourage survey completion. When preferred by participants, surveys were completed in person or by phone to enhance engagement and reduce the likelihood of attrition.

All data at baseline and follow-up timepoints is being collected through online surveys using REDCap (Research Electronic Data Capture), a secure online survey and data capture tool that is hosted at Queen's University.

Electronic health record (EHR) data is being extracted by trained research assistants at the end of the one-year intervention period directly into a securely stored database to capture all primary care provided related to the hip or knee pain. Unique study identifiers are used to link responses from the surveys with data obtained in the EHRs.

At the end of the study, survey responses will be exported from REDCap into encrypted, password-protected datasets and securely stored in Microsoft OneDrive. Data extracted from the EHR, as well as the master list linking participant identifiers to study IDs, will also be kept in encrypted, password-protected files on OneDrive. Audio recordings from qualitative interviews are being transcribed, de-identified, and stored in a secure OneDrive environment at Queen's University.

## **1. Baseline Characteristics Used to Describe the Population**

We collected the following baseline information from participants through REDCap: age, sex, gender, education, duration of hip/knee pain, locations of pain, medications, comorbidities, employment status, income, rurality, and ethnicity. Comorbidities are assessed using the Functional Comorbidity Index (a list of comorbidities that are associated with physical functioning. The presence of a comorbidity is assigned a score of 1 and the total score is the sum of the comorbidity element with a maximum score of 18).

## **2. Individual Health and Experience Outcomes**

The following individual health and experience measures are being collected through REDCap with repeat surveys at baseline, 3-, 6-, 9-, and 12-months post enrollment. Patient satisfaction, global rating of change, and adverse events are being collected at all follow-up time points only.

- Self-reported functioning: using the LEFS – a validated 20-item patient-reported outcome measure used to assess functional status related to lower extremity conditions. Each item is scored on a 5-point scale, with higher scores indicating better function.
- Pain intensity: measured using a Numeric Pain Rating Scale (NPRS) where 0 is no pain and 10 is the worst possible pain.
- Health-related quality of life: using the EuroQOL-5D (EQ-5D-5L), which is suitable for economic evaluations. The EQ-5D-5L score will also be converted to quality-adjusted life years (QALY).
- Global rating of change: using an 11-point global rating of change (GROC) scale to assess perceived overall change in health status, symptoms, or function over time, with anchors of a great deal better (+5) to a great deal worse (-5).
- Patient satisfaction: using an 11-point scale with anchors of very dissatisfied (-5) and very satisfied (+5).
- Adverse events: using an adverse events questionnaire aligned with reporting guidelines. The questionnaire determines: 1) adverse events experienced as a result of any of the interventions received; 2) a description of the adverse event; 3) duration of the adverse event; and 4) severity of the adverse event. Serious adverse events are identified if the participant requires hospitalization or an emergency department as a result of the adverse event, the adverse event leads to significant and persistent disability beyond 72 hours, or the adverse event is life-threatening. The study team monitored these responses to ensure ongoing patient participant safety.
- Potential mechanisms of the intervention:

- Self-efficacy: confidence in abilities to participate in usual activities using the Pain Self-Efficacy Questionnaire (PSEQ).
- Psychosocial risk factors for persistent pain and disability: The Pain Catastrophizing Scale (PCS), Tampa Scale of Kinesiophobia (TSK-11), and 2-item Patient Health Questionnaire (PHQ-2) will measure psychosocial factors associated with pain-related disability.

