The process evaluation will provide an understanding of how the PT-led primary care model for patients with hip and knee pain was implemented, explore the potential mechanisms of the interventions, and capture the experiences of patients who received care through this model.

**Patient and Public Involvement:** A person with lived experience was involved throughout this study, contributing to the conceptualizing the study, study design, and selection of outcomes important to people with lived experience. Their ongoing involvement included pre-testing data collection tools, supporting the interpretation of process evaluation results, and co-developing knowledge mobilization supports such as tailored summaries that will be distributed through patient organizations.

**Enrollment and Randomization of Sites:** We enrolled all 14 Ontario sites from the 20 sites included in our cluster-RCT testing a similar model of care for people with low back pain in Ontario and British Columbia. We used the existing randomization schedule, with a 1:1 ratio of the intervention and comparison arms. Covariate constrained randomization was used by an independent statistician to reduce the risk of baseline imbalances across study arms; the number of active patients and rural versus urban clinic setting were used as covariates. Each cluster name was concealed with a deidentified code prior to randomization. The maximum tolerable difference for rural/urban was 1. The strata balancing criteria was 10% for number of active patients.

**Strategies to Mitigate Bias:** Given the nature of the trial design and the interventions being compared, blinding was not feasible for the PTs, patient participants, primary care team members, or research assistants. While this limitation is inherent to the study design, we implemented several measures recommended for cluster randomized trials to reduce potential bias.

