### **Interventions:**

**PT-Led Primary Care Model for Hip and Knee Pain:** The index intervention incorporates a PT within the primary care team as an option for the first point of contact for people presenting with hip or knee pain for one year from the time of enrolment. Patients in this model are given the choice of seeing the PT or primary care provider first. There are four key components of the PT-led intervention: 1) initial assessment and screening; 2) brief individualized intervention at first visit; 3) health services navigation; 4) and providing additional PT care for people with an unmet need (e.g., no insurance coverage for PT). **Physiotherapist training:** During two consecutive days, seven registered physiotherapists received training on this new model of care to apply across the seven sites randomized to the PT-led primary care model for hip or knee pain.

- 1) Initial assessment and screening: the PT provides a comprehensive patient assessment according to established clinical practice guidelines. The assessment includes taking a detailed clinical history; screening for potential pathology and the need to refer to another HCP; physical examination; and using a validated patient reported outcome measure (LEFS) to guide clinical decision-making.
- 2) Brief individualized intervention at first visit: the PT intervention is at the discretion of the PT to reflect real-world PT practice.
- 3) Health services navigation: where applicable, patient participants are provided with options available to them in their community for rehabilitation programs or other health or social services. For example, they may be referred to community PT for ongoing management or presented with options for group exercise programs. Patients are assessed regarding the need for specialist referrals or resources available to manage complex clinical presentations such as

comorbidity, frailty, or the need for surgical consult. Patients are referred to the primary care provider if specialized services are needed or when the PT cannot provide a direct referral. In addition, patients are referred back to their primary care provider when it is deemed that their clinical needs fall outside of the PT's scope of practice (i.e., medication advice, pathology requiring medical attention) or they identify factors that require mental health intervention.

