### 3. Health System Outcomes

Primary care physician or nurse practitioner visits: the total number of patient visits, both initial and follow-up, related to hip or knee pain. This metric is being used to explore whether involving PTs in care delivery helps alleviate demand on primary care providers, potentially allowing them to allocate more time to patients with other health concerns.

Healthcare utilization within the primary care team: consultations with all primary care team members (e.g., physicians, nurse practitioners, nurses, social workers, and occupational therapists), including the PT in the intervention sites, and group programming accessed within the organization. This data is being collected from the EHR abstraction process.

Healthcare utilization outside of the primary care team: medications used; walk-in clinic visits; ED visits; inpatient hospital stays; diagnostic imaging; surgeries, injections, and other interventional procedures; visits to specialist physicians; and visits to other health professionals outside the primary care team (e.g., chiropractors, massage therapists, occupational therapists, physiotherapists, chronic pain clinics). These outcomes are being collected from the self-report surveys at each follow-up assessment and verified, whenever possible, in the EHR.

Missed Occupational Activities: self-reported time lost from paid employment, volunteer, homemaking, or educational activities.

Assistance required: self-reported paid and unpaid assistance required. For example, self-care (e.g., taking medications, dressing/undressing, going to the bathroom, bathing/showering, grooming), shopping/groceries, meal preparation, housework, managing finances, or transportation (e.g., to a medical appointment).

**Costs:** Total per-person costs include both direct and indirect healthcare costs, with indirect costs estimated using a human capital approach based on time missed from work or other daily activities.

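### Serious adverse events are counted only when an unblinded participant attributes them to an intervention, and the plan does not reconcile them with the ED visits and admissions it collects

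*Combined protocol and SAP*

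**What the plan says.** Under Individual Health and Experience Outcomes, the first item of the adverse event questionnaire covers "adverse events experienced as a result of any of the interventions received"; description, duration and severity follow from it. Seriousness is then defined on the events so reported: "Serious adverse events are identified if the participant requires hospitalization or an emergency department as a result of the adverse event", with persistent disability and threat to life as the other criteria. Timing is given as "Patient satisfaction, global rating of change, and adverse events are being collected at all follow-up time points only", that is, at 3, 6, 9 and 12 months. The only check described is "The study team monitored these responses to ensure ongoing patient participant safety".

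Strategies to Mitigate Bias states that "blinding was not feasible for the PTs, patient participants, primary care team members, or research assistants". Study arm was withheld until consent, so it can be known throughout follow-up.

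Health System Outcomes lists ED visits and inpatient stays among care received outside the primary care team. Of that group it says: "These outcomes are being collected from the self-report surveys at each follow-up assessment and verified, whenever possible, in the EHR". The Data Analysis Plan compares ED visits and hospital admissions between arms as utilization, by robust Poisson regression. Minor adverse events are compared by relative risk, and serious ones are described only.

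**The concern.** Research Objectives lists adverse events among the outcomes on which the two care models are compared. If an event enters the count only when the participant blames an intervention, the count depends on what the participant recognises as an intervention and on what they believe caused the event. The arms may differ in both. The PT-led model gives a distinct assessment and a brief individual intervention at the first visit. Usual care is unstandardized, and a participant might not regard advice or waiting as something received.

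Harm from a late or missed diagnosis is especially hard for a participant to attribute. The PT assessment includes "screening for potential pathology and the need to refer to another HCP", so this is a risk the model itself recognises.

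Hospitalization and ED use are criteria for seriousness and are also recorded as utilization. A participant who reports an admission but no adverse event would appear in the utilization results and not in the safety results. A low serious event count could then be read as reassurance about first-contact PT care without anyone knowing how many recorded ED visits or admissions lie outside it.

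**Working it through.** The plan states no adverse event rate, so there is no figure to reproduce. The check is a comparison of the text, followed by an illustration under assumed values.

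**Text**

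1. Entry condition: attribution to an intervention, made by the participant (Individual Health and Experience Outcomes).
2. Serious events are a subset of step 1, because the hospitalization or ED use must result from the reported adverse event.
3. The reporter is unblinded (Strategies to Mitigate Bias). No causality or seriousness review by anyone unaware of arm is described, and Intervention Modifications says no data monitoring committee was set up.
4. ED visits and inpatient stays are collected in the same follow-up surveys (Health System Outcomes). EHR verification is stated for these outcomes and not for adverse events.
5. Their stated uses are the utilization comparison and costing. No section compares them with the serious event list.
6. Linkage is feasible: Data Collection and Management says study identifiers connect survey and EHR data.
7. Linkage has limits. The EHR extraction covers hip- or knee-related primary care and not hospital care. For ED visits and admissions, the EHR verifies what the survey reported.

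**Illustration**

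Inputs: n = 560 / 2 = 280 per arm, from the required sample size in Study Power and used only for scale. The true serious event risk p is assumed equal in both arms at 2%, 5% or 10%. The probability a that the participant attributes the event is also assumed. Attrition and clustering are ignored.

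Expected counted events per arm = n × p × a. With equal p, the apparent ratio is a₁ / a₂. The share missed over both arms is 1 − (a₁ + a₂) / 2.

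| Attribution (arm 1, arm 2) | p = 2% | p = 5% | p = 10% | Apparent ratio | Missed |
|---|---|---|---|---|---|
| 100%, 100% | 5.6 v 5.6 | 14 v 14 | 28 v 28 | 1.0 | 0% |
| 60%, 60% | 3.4 v 3.4 | 8.4 v 8.4 | 16.8 v 16.8 | 1.0 | 40% |
| 60%, 30% | 3.4 v 1.7 | 8.4 v 4.2 | 16.8 v 8.4 | 2.0 | 55% |

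For example, 280 × 0.05 × 0.60 = 8.4 and 280 × 0.05 × 0.30 = 4.2. Exchanging the arms in the last row gives 0.5. Incompleteness thus needs only a below 100%; a difference between arms also needs a₁ ≠ a₂. The documents fix neither value.

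**The case against.** The strongest reply is that ED visits and hospital admissions are already compared between arms. The Data Analysis Plan specifies relative risks with a small-cluster correction, the covariates of the health outcome analyses and a time offset, and requires no adverse event report. This stands, and it narrows the point: the data will be analyzed. It does not remove the point, because without a match nobody can say how many of these events are also in the serious event list, and the plan does not tie the safety conclusion to them.

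The question is also worded identically for both arms, and only a summary of the questionnaire is given. Intervention Modifications foresees "changes in clinical status, or adverse reactions to medications or exercises", which are things a participant in either arm could attribute. So differential attribution is possible and not shown. The plan describes the questionnaire as following reporting guidelines, but by title the two cited references concern rheumatology triage and access to arthritis care, so the citation does not settle the matter.

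Reconciliation may be done in practice. The documents are silent on it; if it is planned, the SAP need only say so.

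Four stronger readings are tempting and not supported:

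- *Harm from missed pathology is captured nowhere.* A resulting ED visit or admission could appear in the utilization comparison.
- *The ED and admission items are all-cause.* The plan does not say. Physician and nurse practitioner visits in the same section, and the EHR extraction, are limited to hip or knee pain.
- *The EHR can recover survey non-responders.* For them there is no survey report to verify, and no systematic extraction of hospital care is described.
- *The assumed 20% attrition at 12 months is the share of participants without safety data.* They may have answered at 3, 6 or 9 months.

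**Conclusion.** The concern holds in a limited form. As written, the plan can undercount serious adverse events, because an unblinded participant's attribution is the entry condition and no step reconciles the list with the ED visits and inpatient stays collected beside it. A difference between arms is possible if attribution differs, but a reader should not infer that one exists or which arm it would favour. The ratios of 2.0 and 0.5 and the 40% and 55% losses follow from assumed attribution rates and are not estimates for this trial. The plan presents serious events descriptively and computes no such ratio, so the practical risk lies in how the counts by arm are read.

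The primary LEFS analysis is unaffected. The change is worth making because adverse events are part of the first objective and a low serious event count alone cannot support a reassuring safety statement. The verdict assumes that the summary of the questionnaire reflects its actual wording and that no undocumented reconciliation takes place.

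**What to change.** Add to the SAP, before analysis starts:

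1. Match each recorded ED visit and inpatient stay (survey report, with EHR verification where available) to the adverse event questionnaire by study ID and follow-up window.
2. In the serious adverse event table, report by arm (a) participant-attributed serious events, as now, and (b) all participants with a recorded ED visit or admission, with the number of these who reported no adverse event in that window.
3. State whether the ED and admission items are all-cause or limited to hip or knee pain.
4. Give the number of participants with data from each source at each time point, and say that survey non-responders are only partly covered.
5. State that adverse events are participant-attributed and that the safety conclusion rests on (a) and (b) together.

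The cost is SAP wording and a programmed match on data already collected; no survey question changes. Data collection was expected to end on December 19, 2025, with analysis afterwards. The downside is lower specificity: (b) will include unrelated events, and a match within one window does not prove that the two records describe the same event. That is why (b) is shown beside (a) and does not replace it.

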### 3. Health System Outcomes

Primary care physician or nurse practitioner visits: the total number of patient visits, both initial and follow-up, related to hip or knee pain. This metric is being used to explore whether involving PTs in care delivery helps alleviate demand on primary care providers, potentially allowing them to allocate more time to patients with other health concerns.

Healthcare utilization within the primary care team: consultations with all primary care team members (e.g., physicians, nurse practitioners, nurses, social workers, and occupational therapists), including the PT in the intervention sites, and group programming accessed within the organization. This data is being collected from the EHR abstraction process.

Healthcare utilization outside of the primary care team: medications used; walk-in clinic visits; ED visits; inpatient hospital stays; diagnostic imaging; surgeries, injections, and other interventional procedures; visits to specialist physicians; and visits to other health professionals outside the primary care team (e.g., chiropractors, massage therapists, occupational therapists, physiotherapists, chronic pain clinics). These outcomes are being collected from the self-report surveys at each follow-up assessment and verified, whenever possible, in the EHR.

Missed Occupational Activities: self-reported time lost from paid employment, volunteer, homemaking, or educational activities.

Assistance required: self-reported paid and unpaid assistance required. For example, self-care (e.g., taking medications, dressing/undressing, going to the bathroom, bathing/showering, grooming), shopping/groceries, meal preparation, housework, managing finances, or transportation (e.g., to a medical appointment).

**Costs:** Total per-person costs include both direct and indirect healthcare costs, with indirect costs estimated using a human capital approach based on time missed from work or other daily activities.

Direct costs incorporate intervention-related expenses (e.g., physiotherapist salary and training), publicly funded healthcare services (sourced from the Ontario Ministry of Health Schedule of Benefits), medication costs (using the Ontario Drug Benefit formulary), and participant-reported expenses for privately funded services or out-of-pocket supports (e.g., self-care, household help, transportation). Resource use will be multiplied by relevant unit costs to estimate total expenditures, which will be summed over each follow-up interval and used to calculate both time-specific and overall costs.

Indirect costs reflect productivity losses due to time away from paid work, valued using the provincial average wage from Statistics Canada for participants not engaged in paid employment (e.g., retirees, homemakers, caregivers, students). Lost time from unpaid activities will be valued using the minimum wage in Ontario.

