**Corresponding author:**

[name], Associate Professor

School of Rehabilitation Therapy, Queen's University, [name]

[[contact]](mailto:[contact])

**Version date:** November 20, 2025

**Results:** Our internal pilot cluster randomized trial was registered prospectively in February 2023 (NCT05736133). Recruitment of primary care sites (clusters) was completed in June 2023 and cluster randomization was performed in July 2023. Patient recruitment began in October 2023. When progression criteria for patient participant recruitment rate, assessment completion rate, and treatment fidelity were met at the 20-week time-point; the decision was made to progress directly into the fully powered trial without performing any preliminary analysis of the outcome data collected during the pilot phase with the plan to incorporate this data in the full trial analysis. The fully powered trial was registered at ClinicalTrials.gov (NCT06358521) at the end of the pilot phase (April 2024). Participant recruitment was completed in November 2024. At the time of publishing this protocol and analysis plan, data collection is ongoing and expected to be completed by December 19, 2025. Analysis will be conducted as outlined in this pre-specified analysis plan starting after all data collection is complete. No interim analysis was planned or completed. The findings are anticipated to be published in 2026.

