**Data Analysis Plan**

All analyses will be by intention to treat principle. Descriptive statistics will be provided for baseline characteristics and outcomes using means (standard deviation) or medians (interquartile range) for continuous variables and frequencies (percent) for categorical variables. We will compare arms using linear mixed models and generalized estimating equations (GEE) to account for clustering and present the corresponding p-values. Analyses will be performed using SAS, version 9.4 (SAS Institute Inc; Cary, NC).

The estimand for patient health outcomes will be the time-specific patient participant treatment effect, adjusting for clustering by primary care site. The primary outcome (LEFS) will be analyzed using linear mixed regression with restricted maximum likelihood (REML) estimates under the assumption of Missing at Random (MAR), which will allow the use of all available data without the need for multiple imputation. The Kenward-Rogers degrees of freedom correction will be used to account for a small number of clusters. The 12-month timepoint will provide the intervention effect as the adjusted least square mean difference between arms with 95% confidence intervals. Secondary comparisons will be made using adjusted least square mean differences between arms at all intermediate time-points. Fixed effects in the mixed model will include time, intervention group by time interaction (omitting the group main effect), pre-specified covariates associated with hip and knee function (patient participant age, sex, duration of current episode of hip or knee pain, income, highest level of education, and comorbidity score), and primary care site rurality and number of active patients (the covariates from the covariate-constrained allocation procedure). Repeated measures will be modeled using a covariance structure determined by information criteria (AIC/BIC). Clinic site will be included as a random effect to account for site clustering. We will assess for potential risk of bias associated with missing data by comparing the characteristics of those who participated. We plan to carry out a sensitivity analysis for a potential departure of our MAR assumption using a delta-adjusted imputation pattern mixture model approach. This approach will allow us to investigate the robustness of our trial outcomes with regard to the missing values of the LEFS.

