to account for small number of clusters. Given that we have only included 14 clusters and adverse events are expected to be rare, we anticipate there may be issues of non-convergence or instability in our models. Should the model for adverse events not converge or demonstrate instability, we would attempt to fit the model using an independent working correlation matrix. If there are still issues of non-convergence or instability, we will reduce the model by removing covariates, beginning with duration of pain and income. Severity and duration of minor adverse events will be presented descriptively. We do not anticipate many, if any, serious adverse events; as such, we plan to present these data descriptively.

Visits with primary care physicians or nurse practitioners, time (days) lost from occupational activities, and assistance required (hours) will be presented as rates and compared by calculating rate ratios using GEE-type covariance estimators with an adjusted Poisson or negative binomial model, accounting for clustering, and assuming an exchangeable working correlation matrix. Incidence rates will be used to present visits to other health professionals within the primary care team, participation in group programs offered by the primary care team, and health care services received outside of the primary care team (medications, diagnostic imaging, walk-in clinic visits, ED visits, specialist physician visits, , hospital admissions, interventional procedures, surgeries, other health provider visits). Comparisons between groups for each of these variables will be made by calculating relative risk using robust Poisson regression. These models will incorporate empirical covariance (“sandwich”) bias-adjusted (residual-based) estimators, and the Fay and Graubard correction due to the small number of clusters. These models will use time as an offset to account for variable follow-up times. All of the healthcare utilization and lost time from occupational activity models will control for the same covariates as the patient health outcomes analyses. Similar to our analyses for adverse events, in the case of model non-convergence or instability, we will attempt to fit the model using an independent working correlation matrix and if the model still does not converge and demonstrate stability, we will reduce the model by removing covariates.

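### The indirect-cost rule attaches the average wage for lost paid work to participants who have no paid job, and gives no rate for employed participants' lost paid time

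*Combined protocol and SAP*

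**What the plan says.** Section 3 (Health System Outcomes) collects "self-reported time lost from paid employment, volunteer, homemaking, or educational activities". Its Costs paragraph describes "indirect costs estimated using a human capital approach based on time missed from work or other daily activities".

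Two sentences then set the rates. The first concerns productivity loss from absence from paid work, which is "valued using the provincial average wage from Statistics Canada for participants not engaged in paid employment"; students, caregivers, homemakers and retirees are its examples. The second reads: "Lost time from unpaid activities will be valued using the minimum wage in Ontario".

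The Data Analysis Plan says only that quantities of resource use are multiplied by their unit costs. It makes the societal perspective primary for the cost-utility analysis and the health-payer perspective secondary. The Potential Mechanisms section adds a report of the share of costs that comes from missed occupational activities. The Results paragraph at the front commits the team to the plan: "Analysis will be conducted as outlined in this pre-specified analysis plan starting after all data collection is complete".

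**The concern.** The first sentence joins a type of loss (paid work) to a group of people defined by not having that type of work. Taken at its word, it prices something close to empty. Employed participants, who can lose paid time in quantity, are left without a rate.

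Indirect cost enters total societal cost, and through it the incremental cost per QALY, the net benefit at each willingness-to-pay value, the acceptability curves and the cost split under Potential Mechanisms. If the rule is repaired only once the data are in hand, the wage choice is made when its effect on the result can be seen. A pre-specified plan is meant to prevent that.

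**Working it through.** The plan states no figure to reproduce: it gives no wage amounts, lost hours or indirect-cost total. The check is therefore of the text.

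**Step 1. Look for another rate for employed participants' paid time.** The Costs paragraphs and the cost-utility paragraph give none. The baseline section lists "employment status, income, rurality, and ethnicity" among the descriptors, and the Data Analysis Plan uses income as a covariate ("patient participant age, sex, duration of current episode of hip or knee pain, income, highest level of education, and comorbidity score"). Neither place links income to the valuation of lost time.

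**Step 2. Set the possible readings side by side.**

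| Lost time | Literal text | A: rate by type of time | B: own wage, average wage as proxy | C: clause prices the named groups' own time |
|---|---|---|---|---|
| Employed, paid | no rate | average | own wage | no rate |
| Employed, unpaid | minimum | minimum | minimum | minimum |
| Not employed, paid | average, but essentially nothing to price | average, if any | none | none |
| Not employed, unpaid | minimum | minimum | average | average and minimum |

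A requires the qualifier about paid employment to be dropped. B requires an own-wage phrase that is not in the text, and a minimum-wage sentence limited to employed participants. C leaves one cell empty and another with two rates. Only A and B give one rate per cell. They differ in two cells, and neither is what the text says.

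**Step 3. See what can be said about size.** Let the minimum wage be 1 unit per hour and the average wage k. Let ΔP and ΔU be the between-arm differences in mean paid and unpaid hours lost. Incremental indirect cost is then:

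- reading A: k·ΔP + ΔU
- literal text: ΔU
- average wage applied to all lost time: k·ΔP + k·ΔU

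The documents give neither k, ΔP nor ΔU, so neither the size nor the direction of the change in incremental cost can be derived.

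**Step 4. Illustration for total (not incremental) indirect cost.** Assume k = 2 (range 1.5 to 2.5) and a paid share of lost hours p = 0.5 (range 0.25 to 0.75). These values are assumptions and are not in the documents. Under reading A the cost per lost hour is p·k + (1 − p) = 0.5 × 2 + 0.5 = 1.5.

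- Employed paid time left unpriced: the share omitted is p·k / (p·k + 1 − p) = 1 / 1.5 = 67%. The range runs from 0.375 / 1.125 = 33% (p = 0.25, k = 1.5) to 1.875 / 2.125 = 88% (p = 0.75, k = 2.5).
- Average wage also applied to unpaid time, with all unpaid hours belonging to the named groups: the ratio to reading A is k / (p·k + 1 − p) = 2 / 1.5 = 1.33, or 33% higher. The range runs from 1.5 / 1.375 = 1.09 (p = 0.75, k = 1.5) to 2.5 / 1.375 = 1.82 (p = 0.25, k = 2.5).

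**Step 5. Check that the inputs fit a repaired rule.** The analysis section expresses the loss as "time (days) lost from occupational activities". If the wage rates are hourly, days must be converted to hours, and no conversion is given. The activities collected are listed together, and the text does not say that time is recorded separately for each type.

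**The case against.** The strongest reply is that this is a drafting slip with an obvious repair. The main clause ties the average wage to paid work and the next sentence gives unpaid time its own rate, so any competent analyst would use the average wage for paid time and the minimum wage for unpaid time. That is indeed the reading closest to the text. It still requires an explicit qualifier and its four examples to be ignored, and a second repair (own wage for the employed, average wage as proxy for the rest) is plausible and prices two cells differently. The documents do not choose between them.

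Other parts of the reply stand. A reader might infer that employed participants' lost pay will be left out of the analysis. The declared human capital approach covers time missed from work, so that outcome is unlikely even though the literal rule leads to it. A reader might also infer that homemaking or study time is bound to be priced twice. It is not, if the minimum-wage sentence was meant only for employed participants' unpaid activities; but the text does not say so. Finally, the percentages above rest on assumed inputs and describe total cost, so they carry no weight as evidence of bias in the cost-utility result.

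The consequence is also limited by the plan itself: days lost are compared between arms without any wage, and costs are reported disaggregated as well as in total.

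**Conclusion.** The concern holds. The costing rule is wrong as written, and no other section repairs it: it assigns the paid-work rate to people outside paid work and leaves employed participants' lost paid time without one. Confidence is high on the wording and lower on what the sponsor intended.

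The effect is confined to the indirect-cost component of the societal cost-utility analysis and to the cost split under Potential Mechanisms. LEFS, QALYs and direct costs are unaffected. The health-payer analysis is probably little affected, but its cost items are not listed, so this cannot be confirmed.

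The documents do not support a claim that the societal result will be biased by any stated amount or in any stated direction. The point should be corrected before the economic analysis, and it does not threaten the primary effectiveness result.

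**What to change.** Before the economic analysis starts, replace the two sentences with a single rule that gives one rate and one source for each type of lost time and names the participants it applies to. Record the change by the route in the Protocol Amendments paragraph (registry update and description in the final publication).

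The wording closest to the current text would be: time lost from paid employment at the Statistics Canada provincial average wage; all lost unpaid time (volunteer, homemaking, educational, caregiving and other daily activities) at the Ontario minimum wage; the qualifier about participants outside paid employment removed. If the sponsor intended something else, such as own wage for employed participants with the average wage as proxy for others, it should state that rule instead, provided the collected income data allow it.

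The rule should also state how lost days convert to hours, and the sponsor should confirm that paid and unpaid lost time are recorded separately. If they are not, rates by type of time cannot be applied directly and the rule must say what is done.

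The cost is two amended sentences and, optionally, one sensitivity run with the alternative wage. An own-wage rule may need income and hours data that the documents do not show to be available.
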